8.2.1 Clinical Laboratory Evaluations

8.2.1.1 Screening and Safety Clinical Laboratory (Hematology, Chemistry, and Urinalysis) Tests

Blood and urine samples for clinical laboratory tests will be collected at Screening Visit, and on Days -1 (if not collected ≤ 7 days of dosing) and 4, or ET. These tests will include:

- Hematology (HEM): hemoglobin (Hgb), hematocrit (Hct), red blood cell (RBC) count, platelet count, and white blood cell (WBC) count with absolute differential count
- Chemistry (CHEM): serum creatinine, with estimation of GFR, blood urea nitrogen (BUN), glucose (fasting at least 4 h), total bilirubin, direct bilirubin, alanine aminotransferase (ALT), aspartate aminotransferase (AST), alkaline phosphatase (AP), total protein, albumin, sodium, chloride, potassium, bicarbonate (CO_2), magnesium
- Urinalysis (UA): Routine dipstick testing of clean-catch urine for blood, protein, and glucose; other coincidental tests will be recorded

Clinical laboratory tests at Screening Visit and Day -1 should be in the normal reference range with acceptable exceptions, as shown below and in [Appendix B](#):

Elevated bilirubin due to documented Gilbert's syndrome that is Grade 1 is allowable, but Grade 2 or higher is exclusionary. (To document a subject has Gilbert syndrome, a diagnosis from the medical record must be provided or the PI may make a 'presumptive' diagnosis of Gilbert syndrome in subjects with unconjugated hyperbilirubinemia on repeated testing (at least 2 samples separated in time) who have otherwise normal serum ALT/AST and AP concentrations, and a normal CBC.)

Elevated serum glucose, sodium, potassium, bicarbonate (CO₂), total protein, and AP with a toxicity grade of 1 is allowable.

Serum chloride and albumin above the upper limit of normal (ULN) is allowable.

If UA by dipstick is not within acceptable ranges per [Appendix B](#) for blood, protein, or glucose, a complete UA with microscopic evaluation will be performed and the results will supersede those of the dipstick. Menstruating females failing inclusion criteria due to a positive urine dipstick or microscopic UA may be retested following cessation of menses. Do not exclude subjects with ≤ 6 RBC/HPF.

Laboratory values that are outside the range of eligibility but are thought to be due to an acute condition or due to collection or laboratory error may be repeated once.

Laboratory values will be transferred in AdvantageEDCSM.

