they deteriorate after study drug dosing. For abnormalities noted from the time of study drug dosing, any Grade 1 or higher laboratory abnormality listed on the toxicity table in [Appendix C](#) will be entered in the database as an AE. Safety laboratory results that are abnormal according to the local laboratory reference range, but not considered a Grade 1 abnormality, will be evaluated by the study site clinician and reported as Grade 1 abnormality if clinically significant. If not clinically significant, these will not be considered laboratory AEs and will thus not be graded, but will be recorded in the source document and followed-up clinically at the discretion of the study site clinician. Abnormal laboratory values, performed as part of the complete CBC, clinical chemistry or UA but not listed in this toxicity table will be evaluated by the study clinicians, recorded in the source document and, if clinically significant, considered AEs and graded according to the criteria in [Section 9.2.1](#).

Protocol-specific laboratory normal range values in effect at the time of protocol submission are included in [Appendix B](#). Changes in these ranges during the trial will be handled as administrative protocol amendments and toxicity grades will be calculated using the new ranges from the effective date of the change. A regular protocol amendment will be submitted for these changes if a revised laboratory normal range value meets criteria for Grade 2 toxicity.

Gross blood in urine that is confirmed due to a menstrual cycle is not an AE (but is for all other reasons).

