Note 2: Safety laboratory results that are abnormal according to the local laboratory reference range, but not considered a Grade 1 abnormality, will be evaluated by the study site clinician and reported as Grade 1 abnormality if clinically significant. If not clinically significant, these will not be considered laboratory AEs and will thus not be graded, but will be recorded in the source document and followed-up clinically at the discretion of the study site clinician.

Note 3: Other laboratory parameters performed and reported as part of the complete blood count, metabolic panel and urinalysis will be evaluated by the study physician, recorded in the source document, and reported as laboratory AEs if clinically significant, and graded according to the criteria in [Section 9.2.1](#).

Note 4: If US by dipstick is abnormal, a microscopic UA will be performed and the results will supersede the results of the dipstick UA.

Note 5: Menstruating females with a positive urine dipstick or microscopic UA may be retested following cessation of menses.

| ECG interval abnormality | Grade 1 | Grade 2 | Grade 3 |
|--|---|--|---|
| QT/QTc interval (Fridericia's correction) prolonged (msec) | Asymptomatic, QTc 450-479 msec, OR increase in interval <30 msec above baseline | Asymptomatic, QTc 480-499 msec OR increase in interval 30-59 msec above baseline | Asymptomatic, QTc \geq 500 msec OR increase in interval \geq 60 msec above baseline |
| PR interval prolonged - sec | 0.21-0.25 sec | >0.25 sec | Type II 2 nd degree AV block OR ventricular pause >3.0 sec |

Note: The events will be coded as SAE if there are life-threatening associated symptoms or signs (arrhythmia, CHF, hypotension, syncope, torsade's de pointes, etc.)

Note: If a male subject was accepted into the trial with a QT/QTc value that overlaps with values used for grading Grade 1 (mild) QT/QTc prolongation, an AE will be reported if the on-study value of the QT/QTc is higher than the baseline.

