9.6. Clinical Laboratory Evaluations

Toxicity grade criteria can be found in [Table 3](#) and [Table 4](#). Unscheduled or repeated follow-up tests for medical or safety reasons will be listed but excluded from tabular and graphical summaries.

Clinical labs will not be collected for Day -1 if collected ≤ 7 days of dosing. In all cases, the most recent result in the database prior to dosing will be used as baseline. Missing clinical laboratory results on Day 4 or ET will not be imputed. If multiple Day -1 results exist for a subject, the latest result prior to dosing will be regarded as the baseline value.

All clinical laboratory results (chemistry, hematology, and urinalysis) will be listed ([Listing 9](#), [Listing 10](#), and [Listing 11](#)). Other laboratory results (viral serology, pregnancy tests, and confirmation of menopause) will be listed separately ([Listing 12](#)). Toxicology results will be shown in [Listing 13](#) and Breathalyzer results will be shown in [Listing 14](#). Abnormal laboratory results will be listed in [Table 16](#), [Table 17](#), and [Table 18](#).

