Hematology laboratory results will be summarized by parameter and severity (including maximum severity post-baseline) regardless of relatedness ([Table 60](#), [Table 61](#), [Table 62](#), [Table 63](#), [Table 64](#), [Table 65](#), [Table 66](#), [Table 67](#) and [Table 68](#)) and additionally the frequency of *related* laboratory toxicities will be summarized by parameter and severity (including maximum severity post-baseline; [Table 69](#), [Table 70](#), [Table 71](#), [Table 72](#), [Table 73](#), [Table 74](#), [Table 75](#), [Table 76](#) and [Table 77](#)). Summary statistics will be reported by parameter and scheduled visit, including change from baseline ([Table 78](#), [Table 79](#), [Table 80](#), [Table 81](#), [Table 82](#), [Table 83](#), [Table 84](#), [Table 85](#), [Table 86](#), and [Table 87](#)). Individual line plots showing the laboratory result over time will be shown by hematology parameter ([Figure 18](#), [Figure 19](#), [Figure 20](#), [Figure 21](#), [Figure 22](#), [Figure 23](#), [Figure 24](#), [Figure 25](#), [Figure 26](#), and [Figure 27](#)). Subjects will not be labeled in the line plots, as the purpose of the figures is to give an overall trend of trajectory. The following hematology parameters will be included in summaries of severity: hemoglobin, leukocytes, neutrophils, lymphocytes, monocytes, eosinophils, basophils, and platelets. The following hematology parameters will be included in tables of summary statistics

and in graphical plots: hemoglobin, hematocrit, erythrocytes, leukocytes, neutrophils, lymphocytes, monocytes, eosinophils, basophils, and platelets.

Urinalysis laboratory results will be summarized by parameter (protein, glucose, and hemoglobin) and severity (including maximum severity post-baseline) regardless of relatedness (Table 88, Table 89, Table 90, and Table 91) and additionally the frequency of *related* laboratory toxicities will be summarized by parameter and severity (including maximum severity post-baseline; Table 92, Table 93, Table 94, and Table 95). Because urinalysis parameters are not continuous (except for microscopy follow-up parameters in the event of abnormal urine), no tables of summary statistics or line plots will be produced for urinalysis results. If performed, results of microscopy follow-up tests to abnormal urine dipstick tests will be included in listings of urinalysis results.

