Total protein decrease – g/dL	5.2 – 6.0	4.8 – 5.1	<4.8
Albumin decrease – g/dL	2.8 – 3.4	2.5 – 2.7	<2.5
AST increase – U/L	43 – 104	105 – 209	≥210
ALT increase, male – U/L	73 – 179	180 – 359	≥360
ALT increase, female – U/L	45 – 109	110 – 219	≥220
Alkaline phosphatase increase – U/L	151 – 240	241 – 360	>360
Total bilirubin (serum) increase – mg/dL (with other LFTs in the normal range)	1.4 – 2.0	2.1 – 2.5	>2.5
Total bilirubin (serum) increase – mg/dL (accompanied by a >3 x ULN increase in ALT or AST)**	1.4 – 1.6	1.7 – 2.0	>2.0
Hemoglobin decrease, female – g/dL	11.0 – 11.5	9.5 – 10.9	< 9.5
Hemoglobin decrease, male – g/dL	12.0 –13.5	10.0 – 11.9	<10.0
WBC increase – cell/mm ³	11,000 – 15,000	15,001 – 20,000	>20,000
WBC decrease – cell/mm ³	2,500 –3,500	1,500 – 2,499	<1,500
Neutrophils decrease – cell/mm ³	1,200 – 1,399	1,000 – 1,199	<1,000
Lymphocytes decrease – cell/mm ³	750 – 999	500 – 749	<500
Monocytes increase – cell/mm ³	1,101 – 2,000	2,001– 3000	>3,000
Eosinophils increase – cell/mm ³	500 – 750	751 – 1,500	>1,500
Basophils increase – cell/mm ³	201 – 500	501 – 800	>800
Platelets decrease – cell/mm ³	120,000 – 125,000	100,000 – <120,000	<100,000
Urine*			
Protein	1+	2+	>2+

Laboratory AEs	Mild (Grade 1)	Moderate (Grade 2)	Severe (Grade 3)
Glucose	1+	2+	>2+
Blood (dipstick)	1+	2+	>2+
Blood (microscopic) - RBCs per HPF	6-10	11-50	>50 and/or gross blood
WBC (microscopic) – WBC per HPF	5-10	11-50	>50
Bacteria (microscopic)	few	moderate	Many

* Institutional normal reference ranges and allowable ranges at screening are provided in Appendix B of the protocol.
 **ALT, males: >216 U/mL; ALT, females: >132 U/mL; AST, male or female: >126 U/mL)
Note 1: If a subject was accepted into the trial with a laboratory value of an analyte that overlaps with values used for grading Grade 1 (mild) laboratory abnormalities, an AE will be reported if the on-study value of the same analyte is different (worse) from the baseline.
Note 2: Safety laboratory results that are abnormal according to the local laboratory reference range, but not considered a Grade 1 abnormality, will be evaluated by the study site clinician and reported as Grade 1 abnormality if clinically significant. If not clinically significant, these will not be considered laboratory AEs and will thus not be graded, but will be recorded in the source document and followed-up clinically at the discretion of the study site clinician.

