Note 3: Other laboratory parameters performed and reported as part of the complete blood count, metabolic panel and urinalysis will be evaluated by the study physician, recorded in the source document, and reported as laboratory AEs if clinically significant, and graded according to the criteria in Section 9.2.1 of the protocol.
Note 4: If US by dipstick is abnormal, a microscopic urinalysis will be performed and the results will supersede the results of the dipstick urinalysis.
Note 5: Menstruating females with a positive urine dipstick or microscopic urinalysis may be retested following cessation of menses.

ECG interval abnormality	Grade 1	Grade 2	Grade 3
QT/QTc interval (Fridericia’s correction) prolonged (msec)	Asymptomatic, QTc 450-479 msec, OR increase in interval <30 msec above baseline	Asymptomatic, QTc 480-499 msec OR increase in interval 30-59 msec above baseline	Asymptomatic, QTc ≥500 msec OR increase in interval ≥60 msec above baseline
PR interval prolonged - sec	0.21-0.25 sec	>0.25 sec	Type II 2 nd degree AV block OR ventricular pause >3.0 sec

Note: The events will be coded as SAE if there are life-threatening associated symptoms or signs (arrhythmia, CHF, hypotension, syncope, torsade’s de pointes, etc.)
Note: If a male subject was accepted into the trial with a QT/QTc value that overlaps with values used for grading Grade 1 (mild) QT/QTc prolongation, an AE will be reported if the on-study value of the QT/QTc is higher than the baseline

14.1 Description of Study Subjects**14.1.1 Disposition of Subjects****Table 5: Subject Disposition**

Subject Disposition	All Subjects (N=X)	
	n	%
Screened	x	--
Enrolled	x	100
Received Treatment	x	Xx
Completed Final Blood Draw		
Completed Follow-up (Study Day 8)		
Early Termination ^a		
Discontinued Study Product		

Note: N = number of subjects enrolled

^a Refer to Listing 1 for reasons subjects discontinued or terminated early.

Table 6: Analysis Populations

Analysis Populations	Reason Subjects Excluded	All Subjects (N=X)	
		%	N
Safety Population	Subject not dosed	x	Xx
PK Analysis Population	Any Reason		
	Subject not dosed		
PK Subset	No measurable PK concentration		
	Any Reason		
	Subject not dosed		
	Disqualifying protocol deviation		
	No measurable PK concentration		

Note: N = number of subjects enrolled

Table 7: Ineligibility Summary of Screen Failures

Inclusion/Exclusion Category	Inclusion/Exclusion Criterion	n ^a	% ^b

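### As written, SAP 9.6 can leave a dipstick blood grade in the urinalysis severity tables after microscopy has superseded it, contrary to the SAP's own Table 4 and the protocol

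*SAP*

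**What the plan says.** **Grading rule.** Under protocol 8.2.1.1, when dipstick blood, protein or glucose is outside the Appendix B limits, "a complete UA with microscopic evaluation will be performed and the results will supersede those of the dipstick". An Appendix B footnote repeats this. Note 4 of Appendix C, the on-study grading table, says that "a microscopic UA will be performed and the results will supersede the results of the dipstick UA". The SAP adopts the same rule in Note 4 to its Table 4: "a microscopic urinalysis will be performed and the results will supersede the results of the dipstick urinalysis". SAP 9.6 points to Tables 3 and 4 for its grades.

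Table 4 has two scales for urine blood:
- dipstick: 1+, 2+ and >2+ for Grades 1, 2 and 3;
- the row "Blood (microscopic) - RBCs per HPF": 6-10, 11-50, and >50 or gross blood for Grades 1, 2 and 3.

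It also grades microscopic WBC and bacteria.

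**Tabulation rule.** SAP 9.6 states: "Urinalysis laboratory results will be summarized by parameter (protein, glucose, and hemoglobin) and severity". These are Tables 88-91, with Tables 92-95 for treatment-related results. If microscopy is performed, its "results of microscopy follow-up tests to abnormal urine dipstick tests will be included in listings of urinalysis results". A general sentence near the start of 9.6 adds: "Unscheduled or repeated follow-up tests for medical or safety reasons will be listed but excluded from tabular and graphical summaries".

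Two other provisions bear on the point. For the *Any Parameter* tables, 9.6 takes the highest severity over all results in the category. The Table 19 and Table 32 shells, which Tables 88-95 copy, carry a footnote that brings unscheduled assessments into the maximum-severity row.

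**The concern.** The analytes that 9.6 names for the severity tables are the three dipstick analytes (hemoglobin corresponds to dipstick blood). Nothing in 9.6 carries Note 4 into those tables. A programmer who follows the tabulation sentences would grade the dipstick. A site that follows Note 4 would grade the microscopy.

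The two can then conflict in one report. Protocol 9.2.4 has every graded laboratory abnormality entered as an AE, and SAP 9.3.2 puts laboratory AEs into the AE tables. A subject whose dipstick was overturned would have no AE but would appear with a toxicity in Tables 88 and 91. The baseline row is exposed too, because 8.2.1.1 lets microscopy override the dipstick when eligibility is judged.

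**Working it through.** The plan gives no figure to reproduce. The check applies the Table 4 cut-offs under each rule.

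**1. Two worked cases**

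| Dipstick blood | Microscopy | Grade under Note 4 | Grade if the dipstick is tabulated |
|---|---|---|---|
| >2+ | 3 RBC/HPF | none | 3 |
| 1+ | 30 RBC/HPF | 2 | 1 |

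The first is an overturned toxicity reported as severe. The second is under-graded.

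**2. All combinations.** Each cell says how the dipstick grade compares with the microscopic grade that should replace it.

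| Dipstick (grade) | <6 RBC/HPF (none) | 6-10 (1) | 11-50 (2) | >50 (3) |
|---|---|---|---|---|
| trace (none) | same | too low | too low | too low |
| 1+ (1) | overturned | same | too low | too low |
| 2+ (2) | overturned | too high | same | too low |
| >2+ (3) | overturned | too high | too high | same |

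The trace row applies only if trace triggers microscopy. Protocol 8.2.1.1 triggers on values outside the acceptable range, and Appendix B accepts trace. The Appendix B footnote and both Notes 4 trigger on an abnormal dipstick, and the reference value is negative.

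- From 1+ upward: 12 pairs, of which 3 same, 3 overturned, 3 too high and 3 too low. The grades differ in 3 + 3 + 3 = 9 of 12.
- With trace included: 16 pairs, of which 4 same, 3 overturned, 3 too high and 6 too low. The grades differ in 3 + 3 + 6 = 12 of 16.

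These are counts of possible pairs, not probabilities. The documents give no basis for how often each pair would occur.

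**3. Do the maximum rules repair this?** Let d be the dipstick grade and m the microscopic grade. Note 4 requires m. A maximum rule reports max(d, m), which is wrong whenever d > m.

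- >2+ with 3 RBC/HPF: max(3, 0) = 3, but 0 is required.
- 1+ with 30 RBC/HPF: max(1, 2) = 2, as required.
- Over the grid, d > m in 3 overturned + 3 too high = 6 pairs, under either trigger.

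So where a maximum rule applies, it can repair under-grading but leaves every overturned or over-graded dipstick in place. Its reach is also limited. The *Any Parameter* rule covers Tables 88 and 92. The footnote concerns only the maximum row. For Tables 91 and 95 the SAP does not say that a microscopic RBC count belongs to the hemoglobin parameter.

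**4. Weight of one subject.** With eight subjects in the safety population, 1/8 = 12.5 percentage points. If the population were 7, 1/7 = 14.3 points. If replacement of dosed subjects took it to 10, 1/10 = 10.0 points.

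**The case against.** The strongest reply is that the SAP never says it grades on the dipstick. Section 9.6 takes its grades from Table 4, and Note 4 is part of Table 4, so a careful programmer would apply it. The microscopy sentence does not say listings only, and it follows an explanation of why there are no summary statistics or line plots. Whether a protocol-required microscopy counts as a repeated follow-up test is not stated. With about eight subjects every result is listed, Table 18 lists abnormal urinalysis results with severity, and laboratory AEs reach the AE tables separately.

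Much of this stands. The SAP contains the supersede rule, so the conflict lies inside the SAP and is not a plain departure from the protocol. No safety data are lost, and a reader of the listings could find a discrepancy.

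The reply does not remove the conflict. Section 9.6 itself calls microscopy a follow-up test, so its exclusion sentence reads naturally as covering it. The maximum rules are not replacement rules, as step 3 shows. A correct listing does not correct a wrong cell in a summary table.

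**Conclusion.** The point holds for urine blood, in Tables 88, 91, 92 and 95. Two stated SAP rules give different grades for the same subject, in either direction, at 12.5 points per subject if N = 8. It rests on the tabulation sentences being programmed as they read, and on at least one subject having discordant dipstick and microscopy results. It should be settled before programming. Its consequence is limited to the accuracy of the laboratory severity tables and their agreement with the AE tables.

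A reader might infer more, but the documents do not support it:

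- **That all urinalysis tables are affected.** Protein and glucose have no microscopic grade scale, so no such error is shown for Tables 89, 90, 93 and 94.
- **That confirmed toxicities are missed.** A graded dipstick that microscopy confirms is still counted, perhaps at the wrong grade. A blood finding would go ungraded in Table 91 only from a trace dipstick, and only under the broader trigger.
- **That microscopic WBC and bacteria grades are never tabulated.** They have no table of their own, but the *Any Parameter* rule could admit them to Table 88.
- **That menstrual blood should count as no toxicity here.** Protocol 9.2.4 says "Gross blood in urine that is confirmed due to a menstrual cycle is not an AE". That covers confirmed gross blood and AE status, whereas Tables 88-91 grade results regardless of relatedness. Any estimate of how often this would arise needs figures from outside the documents.
- **That the SMC's advice on the 4-g dose depends on these tables.** Protocol 9.6.2 leaves review procedures to the charter, and neither document says these tables go to the SMC.

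**What to change.** In SAP 9.6 and the shells for Tables 88, 91, 92 and 95:

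1. State that when follow-up microscopy was performed, its RBC grade from Table 4 replaces the dipstick blood grade in the visit rows (baseline included) and the maximum row. Keep the dipstick value in Listing 11.
2. State that microscopic WBC and bacteria grades count in *Any Urinalysis Parameter*.
3. Reconcile the exclusion of unscheduled and repeated follow-up tests with the Table 19 footnote (repeated under Table 32), which includes unscheduled assessments in the maximum row. Say expressly that the required microscopy is not caught by the exclusion.

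Because item 1 depends on microscopy having been performed, it works under either wording of the trigger. The cost is SAP wording and one derivation rule. The microscopy results are already planned for listing, so this needs no new data and no protocol change.
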